### **7.2.6.3 Hepatic Function Abnormality**

Hy's Law: Cases where a patient shows elevations in liver biochemistry may require further evaluation and occurrences of AST or ALT  $\geq 3 \times$  ULN together with total bilirubin  $\geq 2 \times$  ULN may need to be reported as SAEs.

Hepatic function abnormality (as defined in Section 10.1.3.) in a study subject, with or without associated clinical manifestations, is required to be reported as "hepatic function abnormal" **within 24 hours of knowledge of the event** to the sponsor and AstraZeneca/MedImmune Patient Safety using the designated Safety e-mailbox (refer section 7.3.3.4), unless a definitive underlying diagnosis for the abnormality (e.g., cholelithiasis or bile duct obstruction) that is unrelated to investigational product has been confirmed.

If the definitive underlying diagnosis for the abnormality has been established and is unrelated to investigational product, the decision to continue dosing of the study subject will be based on the clinical judgment of the investigator. If

no definitive underlying diagnosis for the abnormality is established, dosing of the study subject must be interrupted immediately. Follow-up investigations and inquiries must be initiated by the investigational site without delay. Each reported event of hepatic function abnormality will be followed by the investigator and evaluated by the sponsor and AstraZeneca/MedImmune

#### **7.2.8 Unanticipated Problems Involving Risks to Subject or Others**

A UPIRSO is a type of SAE that includes events that meet ALL of the following criteria:

- Is *unanticipated* in terms of nature, severity, or frequency
- Places the research subject or others at a different or *greater risk of harm*
- Is deemed to be *at least possibly related* to participation in the study.

### **7.3 Adverse Event Reporting**

#### **7.3.1 Routine Reporting**

All routine adverse events, such as those that are expected, or are unlikely or definitely not related to study participation, are to be reported on the appropriate eCRF according to the time intervals noted in the appendices. Routine AEs will be reviewed by the Data Monitoring Committee (DMC) according to the study's phase and risk level, as outlined in the DSMP.

#### **7.3.2 Determining if Expedited Reporting is Required**

This includes all events that occur within 30 days of the last dose of protocol treatment. Any event that occurs more than 30 days after the last dose of treatment and is attributed (possibly, probably, or definitely) to the agent(s) must also be reported accordingly.

- 1) Identify the type of adverse event using the NCI CTCAE v 4.03.
- 2) Grade the adverse event using the NCI CTCAE v 4.03.
- 3) Determine whether the adverse event is related to the protocol therapy. Attribution categories are as follows:
  - Definite: AE is clearly related to the study treatment.
  - Probable: AE is likely related to the study treatment.
  - Possible: AE may be related to the study treatment.
  - Unlikely: AE not likely to be related to the study treatment.
  - Unrelated: AE is clearly NOT related to the study treatment.
- 4) Determine the prior experience of the adverse event. Expected events are those that have been previously identified as resulting from administration of the agent. An adverse event is considered unexpected, for expedited reporting purposes only, when either the type of event or the severity of the event is not listed in:
  - the current protocol
  - the drug package insert
  - the current Investigator's Brochure

#### **7.3.3 Expedited Reporting of SAEs/Other Events**

##### **7.3.3.1 Reporting to the Northwestern University QAM/DMC**

All SAEs must be reported to the assigned Quality Assurance Monitor (QAM) within 24 hours of becoming aware of the event. Completion of the NU CRO SAE Form is required.

The completed form should assess whether or not the event qualifies as a UPIRSO. The report should also include:

- Protocol description and number(s)
- The patient's identification number
- AE (verbatim)
- A description of the event, severity, treatment, and outcome (if known)
- The date when the AE started and stopped

- Supportive laboratory results and diagnostics
- The hospital discharge summary (if available/applicable)

All SAEs will be reported to, and reviewed by, the DMC at their next meeting.

The following variables will be collected for SAEs as applicable:

- Date AE met criteria for serious AE
- Date Investigator became aware of serious AE
- AE is serious due to
- Date of hospitalization
- Date of discharge
- Probable cause of death
- Date of death
- Autopsy performed
- Description of AE
- Causality assessment in relation to Study procedure(s)
- <<Causality assessment in relation to Additional Study Drug>>

#### **7.3.3.2 Reporting to the Northwestern University IRB**

*The following information pertains to the responsibilities of the lead site (Northwestern University). Additional participating sites should follow their local IRB guidelines for reporting to their local IRBs (if applicable).*

- Any death of an NU subject that is unanticipated in nature and at least possibly related to study participation will be promptly reported to the NU IRB within 24 hours of notification.
- Any death of an NU subject while on treatment regardless of expectedness or relationship to study drug will be promptly reported to the NU IRB within 24 hours of notification.
- Any death of a non-NU subject that is unanticipated and at least possibly related and any other UPIRSOs will be reported to the NU IRB within 5 working days of notification.
- All other deaths of NU subjects not previously reported, other non-NU subject deaths that were unanticipated and unrelated, and any other SAEs that were not previously reported as UPIRSOs will be reported to the NU IRB at the time of annual continuing review.

#### **7.3.3.3 Reporting to the FDA (completed by the NU QAM)**

The NU QAM will handle all FDA reporting in accordance with the following:

The FDA will be notified within 7 calendar days of any SAE that is associated with study treatment, is unexpected, and is fatal or life-threatening.

The FDA will be notified within 15 calendar days of any SAE that is associated with the study treatment, unexpected, and serious but *not fatal or life-threatening*. This includes any previous SAEs that were not initially deemed reportable, but are later determined to meet the criteria for reporting (i.e. by the DMC).

All other SAEs will be reported on an annual basis as part of the annual FDA report.

#### **7.3.3.4 Reporting to MedImmune**

All deaths that occur during the study, or within the protocol-defined 30-day

post-last dose of durvalumab + tremelimumab safety follow-up period must be reported to AstraZeneca as follows:

- Death that is clearly the result of disease progression should be documented but should not be reported as an SAE.
- Where death is not due (or not clearly due) to progression of the disease under study, the AE causing the death must be reported to AstraZeneca as a SAE within **24 hours** (see Section **Error! Reference source not found.** for further details). The report should contain a comment regarding the co-involvement of progression of disease, if appropriate, and should assign main and contributory causes of death.
- Deaths with an unknown cause should always be reported as a SAE.

All SAEs will be reported, whether or not considered causally related to the investigational product, or to the study procedure(s). The reporting period for SAEs is the period immediately following the time that written informed consent is obtained through 90 days after the last dose of durvalumab + tremelimumab or until the initiation of alternative anticancer therapy. The investigator and/or Sponsor are responsible for informing the Ethics Committee and/or the Regulatory Authority of the SAE as per local requirements.

The investigator and/or sponsor must inform the FDA (as outlined above), of any serious or unexpected adverse events that occur in accordance with the reporting obligations of 21 CFR 312.32, and will concurrently forward all such reports to AstraZeneca. A copy of the MedWatch report must be faxed to AstraZeneca at the time the event is reported to the FDA. It is the responsibility of the sponsor to compile all necessary information and ensure that the FDA receives a report according to the FDA reporting requirement timelines and to ensure that these reports are also submitted to AstraZeneca at the same time.

A **cover page** should accompany the **MedWatch** form indicating the following:

- “Notification from an Investigator Sponsored Study”
- The investigator IND number assigned by the FDA
- The investigator’s name and address
- The trial name/title and AstraZeneca ISS reference number (ESR-14-10694 (D4190C00030)

Sponsor must also indicate, either in the SAE report or the cover page, the **causality** of events ***in relation to all study medications*** and if the SAE is ***related to disease progression***, as determined by the principal investigator.

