### 7.2.2 Severity of AEs

All non-hematologic adverse events will be graded according to the NCI Common Terminology Criteria for Adverse Events (CTCAE) version 4.03. The CTCAE v4.03 is available at <http://ctep.cancer.gov/reporting/ctc.html>

If no CTCAE grading is available, the severity of an AE is graded as follows:

- Mild (grade 1): the event causes discomfort without disruption of normal daily activities.
- Moderate (grade 2): the event causes discomfort that affects normal daily activities.
- Severe (grade 3): the event makes the patient unable to perform normal daily activities or significantly affects his/her clinical status.
- Life-threatening (grade 4): the patient was at risk of death at the time of the event.
- Fatal (grade 5): the event caused death.

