### 7.2.3 Serious Adverse Events (SAEs)

All SAEs, regardless of attribution, occurring from time of signed informed consent, through 30 days after the last administration of study drug, must be reported upon discovery or occurrence.

An SAE is defined in regulatory terminology as any untoward medical occurrence that:

- **Results in death.**  
If death results from (progression of) the disease, the disease should be reported as event (SAE) itself.
- **Is immediately life-threatening.**  
The patient was at risk of death at the time of the event; it does not refer to an event that hypothetically might have caused death if it were more severe.
- **Requires *in-patient hospitalization or prolongation of existing hospitalization for ≥ 24 hours.***
- **Results in persistent or significant disability or incapacity.**
- **Is a congenital anomaly/birth defect.**
- **Is an important medical event.**

Any event that does not meet the above criteria, but that in the judgment of the investigator jeopardizes the patient, may be considered for reporting as a serious adverse event. The event may require medical or surgical intervention to prevent one of the outcomes listed in the definition of "Serious Adverse Event".

For example: allergic bronchospasm requiring intensive treatment in an emergency room or at home; convulsions that may not result in hospitalization; development of drug abuse or drug dependency.

The causality of SAEs (their relationship to all study treatment/procedures) will be assessed by the investigator(s) and communicated to AstraZeneca.

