### **10.0 STATISTICAL CONSIDERATIONS**

#### **10.1 Study Design/Study Endpoints**

This will be a single-arm, open-label, pilot phase II study to assess the efficacy and safety of durvalumab in combination with tremelimumab in patients with stage IV breast cancer which is HER2 negative. Patients who have completed the week 16 CT or nuclear bone scan will be evaluable for response endpoints. (*Note: Bone scans will be done only if the patient has bone disease. PET-CT is acceptable in place of bone scan, if a bone scan is contra-indicated for a patient's disease. The same modality used at baseline should be used throughout.*)

The **primary endpoint** is ORR, defined as number (%) of patients with at least one visit response of partial response (PR) plus complete response (CR) in patients with metastatic HER2 negative breast cancer treated with durvalumab in combination with tremelimumab using the Response Evaluation Criteria in Solid Tumors (RECIST) Version 1.1 (23). Any patient who has completed two months of study therapy is evaluable for this end point.

**Secondary endpoints** include PFS and OS, where PFS is defined as the time from date of treatment initiation until date of documented disease progression or death (by any cause in the absence of progression), and OS is defined as the time from date of treatment initiation until death due to any cause. Clinical benefit rate (SD for  $\geq$  12 weeks + PR + CR) will be assessed. Any patient who has completed two months of study therapy is evaluable for this end point.

The safety endpoints will be the number, frequency, and severity of adverse events (as defined by the NCI Common Terminology Criteria for Adverse Events or CTCAE version 4.03) will be recorded. Any patient treated with minimum 1 dose of either study drug will be evaluable for toxicity.

The expansion cohort will follow a similar design but only include patients with metastatic TNBC. Responses will be captured by RECIST v1.1.

**Exploratory endpoints** include serum and tissue-based biomarkers including: circulating tumor DNA, immunohistochemical expression of PD-L1; TILs; changes in tissue and peripheral T cell receptor sequencing, mutational and neoantigen burden, and immune-related candidate gene signatures at baseline.

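### Sections 7.2.3 and 7.3.3.4 give opposite rules on whether a death from disease progression is reported as an SAE, so the SAE count depends on which section is followed

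*Combined protocol and SAP*

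**What the plan says.** Section 7.2.3 defines an SAE for the whole trial. Under the criterion for events resulting in death it says: "If death results from (progression of) the disease, the disease should be reported as event (SAE) itself". The same section requires SAEs to be reported whatever their attribution, and ends: "The causality of SAEs (their relationship to all study treatment/procedures) will be assessed by the investigator(s) and communicated to AstraZeneca".

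Section 7.3.3.4, on reports to the drug supplier, covers deaths during the study or within 30 days of the last dose. It says: "Death that is clearly the result of disease progression should be documented but should not be reported as an SAE". Deaths not due, or not clearly due, to progression are to be reported as SAEs, and deaths of unknown cause always are. Further on, the section requires every SAE to be reported regardless of causality. It also asks the sponsor to state whether an SAE is related to progression.

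Section 7.3.3.1 adds: "All SAEs will be reported to, and reviewed by, the DMC at their next meeting".

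On analysis, section 10.1 says: "The safety endpoints will be the number, frequency, and severity of adverse events" (as defined by CTCAE), with this denominator: "Any patient treated with minimum 1 dose of either study drug will be evaluable for toxicity". Sections 10.1 and 10.3 do not say how deaths from progression are counted.

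**The concern.** The same death is an SAE under one section and not reported as one under another. In metastatic disease, deaths from progression on or soon after treatment are foreseeable, and section 4.1.1 allows treatment to continue after suspected pseudoprogression.

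SAE status decides what goes to the quality monitor within 24 hours and to the DMC (7.3.3.1), to the IRB at continuing review (7.3.3.2), to the FDA in the annual report (7.3.3.3) and to the supplier (7.3.3.4). Two coordinators following different sections would produce different SAE listings from identical patients. A reader of the final safety table could not tell whether its fatal SAEs include deaths from the cancer itself. In cohorts this small, one or two such deaths would visibly change the table.

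**Working it through.** No figure in the plan needs reproducing. The check is a comparison of the two rules, followed by simple arithmetic on scale.

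**1. Do the rules cover the same event?** Yes. Both address a death caused by progression. Section 7.2.3 makes the disease, rather than the death, the reported event, but an SAE still results. Section 7.3.3.4 produces none.

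**2. Do they address different recipients, so that both can hold?** Not on the text. Section 7.2.3 is not confined to internal reporting, because it sends SAE causality to the supplier. Section 7.3.3.4 says all SAEs are reported whether or not causally related, so an event that is an SAE under 7.2.3 falls within its scope. Its request to state whether an SAE is related to progression also presupposes that some progression-related events arrive as SAEs.

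**3. Does anything else reconcile them?**
- Section 7.2.4 lists exceptions to the AE and SAE definitions. Neither progression nor death from progression is among them.
- Sections 7.1, 7.3.2 and 7.3.3.5 deal with follow-up, expedited reporting and recording periods, and give no rule for deaths from progression.
- Sections 10.1 and 10.3 give no counting rule.

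Appendix E records that the death-reporting instructions in 7.3.3.4 came in with Amendment 8. That may be how the two rules came to stand side by side.

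**4. Size.** Let d be the number of patients whose death is clearly due to progression inside the reporting window, and n the number treated.
- Difference in SAE count between the rules = d.
- Difference in the share of patients with a fatal SAE = d/n, if the SAE under 7.2.3 is recorded with a fatal outcome.
- Per death with n = 20 (planned expansion cohort): 1/20 = 5.0 percentage points.
- Per death with n = 30 (planned general cohort, Study Summary): 1/30 = 3.3 percentage points.
- The share of patients with any SAE moves by the same amount only if the patient has no other SAE.

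The documents do not give d. It can lie anywhere from 0 to n. It also depends on the window, which is itself stated differently: 30 days after the last dose in 7.2.3 and in the death rule of 7.3.3.4; 90 days in 7.1 and 7.3.3.5; and 90 days or the start of alternative anticancer therapy for SAEs in 7.3.3.4.

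**5. Grade 5.** Section 7.2.2 has "Fatal (grade 5): the event caused death", but only as a fallback where CTCAE offers no grading. Section 7.3.3.4 says such a death is documented, without saying whether progression is entered as a graded AE. The grade 5 count changes only if progression is entered as a fatal AE under one rule and not under the other.

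**The case against.** The strongest defence is that 7.3.3.4 is an instruction about one recipient and not a definition. On that reading 7.2.3 governs classification and the DMC channel, while 7.3.3.4 trims what the supplier is sent. It is true that 7.3.3.4 does not redefine an SAE, and a reader should not infer that it does. But the supplier-only reading does not survive the rest of 7.3.3.4 or the last sentence of 7.2.3, for the reasons in step 2.

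A second defence is that treatment-related deaths remain visible. Much of this stands. Section 7.3.3.4 routes every death of unclear or unknown cause into the SAE stream and asks for main and contributory causes. Section 7.3.3.1 collects probable cause of death for SAEs. Section 7.3.3.2 sends every on-treatment death of a lead-site patient to the IRB within 24 hours, whatever the cause. The disputed group is only deaths clearly due to progression, so the documents do not support a claim that treatment-related deaths go unreported.

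Third, the safety endpoint concerns adverse events, and there is no separate SAE-rate endpoint. That is correct and limits the consequence to safety reporting and tables.

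Finally, Appendix E says the study closed on 7.20.2020 for low accrual. Rewording the protocol cannot alter reports already made. A counting rule for the final tables is still useful.

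**Conclusion.** The inconsistency is real and unresolved in the current text. Its direct effect is on the SAE count and on what the DMC and the supplier receive. Both differ by the number of deaths clearly due to progression inside the window. That number is unknown; each such death shifts the fatal-SAE share by 5.0 points of 20 or 3.3 points of 30. These steps use planned cohort sizes. The actual denominator is patients given at least one dose, which may differ.

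Three stronger readings are tempting but unsupported.
- **That the grade 5 count necessarily changes.** It may, but the documents do not say whether progression is graded as an AE under either rule.
- **That the effect can be sized from the 11 of 18 interim patients with PD in section 1.7.3.** The documents give no rate of death within the window. One of the 11 had pseudoprogression and was still on study at 10 months. The SAE period in 7.3.3.4 also ends when alternative therapy begins, so later disease deaths may fall outside it.
- **That efficacy conclusions are affected.** ORR does not use SAE status. PFS and OS count death from any cause, and the design's error rates concern response only.

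**What to change.** Reconcile 7.2.3 and 7.3.3.4 into one rule on whether a death from progression is reported as an SAE. Apply it to all recipients and state the window to which it applies. If an exception is intended, list it in 7.2.4. Say also whether progression is entered as a graded AE. The choice of rule is for the sponsor and the supplier; what matters for the analysis is that there is only one.

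In the 10.3 safety summary, tabulate deaths from progression in their own row, apart from all other SAEs and fatal events. The treatment-related fatal count then does not depend on which section was followed when the event was reported.

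The cost is a few sentences of protocol wording and one table row. Because enrolment has closed, it also means checking the recorded cause of each death in the window so that past events are classified consistently. No treatment, visit or sample size changes.

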***Send SAE report and accompanying cover page by way of email to AstraZeneca’s designated mailbox:***  
[[contact]](mailto:[contact])

If a non-serious AE becomes serious, this and other relevant follow-up information must also be provided to AstraZeneca and the FDA. Serious adverse events that do not require expedited reporting to the FDA still need to be reported to AstraZeneca preferably using the MedDRA coding language for serious adverse events. This information should be reported on a monthly basis and under no circumstance less frequently than quarterly.

### **7.3.3.5 Study recording period and follow-up for adverse events and serious adverse events**

Adverse events and serious adverse events will be recorded from time of signature of informed consent, throughout the treatment period and including the follow-up period (90 days after the last dose of durvalumab + tremelimumab).

During the course of the study all AEs and SAEs should be proactively followed up for each subject. Every effort should be made to obtain a resolution for all events, even if the events continue after discontinuation/study completion.

If a subject discontinues from treatment for reasons other than disease progression, and therefore continues to have tumor assessments, drug or procedure-related SAEs must be captured until the patient is considered to have confirmed PD and will have no further tumor assessments.

The investigator is responsible for following all SAEs until resolution, until the subject returns to baseline status, or until the condition has stabilized with the expectation that it will remain chronic, even if this extends beyond study participation.

